3.0 Benefits of participation in the study

Individuals that participate may benefit from CCT. The Aims are designed to examine the impact of CCT with or with *PRIIS* to improve cognitive function as well as ADL. Cognitive training programs has been shown efficacious for PD patients as well as patients with other pathologies including TBI and stroke cholinesterase inhibitor medication²³. The information gained in this project will be utilized for further treatment development for cognitive function in Veterans with PD. These pilot data will be used as preliminary data for a larger-scale Merit grant proposal submitted to the VA RR&D service.

4.0 Alternatives to participation

The alternative to participation is to not participate in the study. Participation is entirely voluntary and the participant may withdraw at any time for any reason

5.0 Data Analysis

All test administrators will undergo the same training. Data will be cleaned and tested for normality (if normality tests fail, appropriate transformations will be made), and proper missing data imputation techniques will be used. Test for multicollinearity will be made. The 3 treatment groups will be characterized using descriptive statistics for demographic factors, disease-related variables, and medication use. Groups will be examined for comparability according to the descriptive variables using ANCOVA and mixed-effects model with random subject effects. For ANCOVA, type I error rate ($\alpha=0.05$) will be adjusted for multiple comparisons using Bonferroni corrections.

Neuropsychological Data Analytical Approaches. For Aims 2 and 3, data will be analyzed using a two-level longitudinal mixed effects model with random subject effects to incorporate correlation of measurements nested within the same subject. Covariates will include medication dose, anxiety, apathy, and depression level. Parameters will be estimated using measurements from baseline, endpoint, and follow-up. The group by time interaction parameter will be used to examine the difference of the trends between the three groups. Significance of this parameter will indicate that treatment is efficacious in terms of EF over time when adjusted by covariates. To assess immediate effects of CCT, an experiment group contrast will be formed using test score means at baseline and endpoint and a control group contrast will be made with those same types of means. To assess sustainability of CCT effects, contrasts using means of test scores at endpoint and follow-up will be made for each group. Estimates of variance components from mixed-model analysis will be used to calculate test statistics. Data analysis will be performed using SAS 9.3 Proc Mixed. This modeling process will be reported for each outcome of interest in Aims 2 and 3. Potential moderators of the effects of the CCT will be explored through Pearson correlations and regression analyses. Factors include, age, age at PD onset, disease duration, MoCA score, depression, anxiety, apathy, L-dopa equivalent dose, PD-MCI subtype diagnosis,

scores on training perception, prior computer use and cognitive training. Co-morbidities and medications will be considered as confounders.

MCID for the NIH-EXAMINER executive composite score will be computed using two anchor-based MCID approaches. First, a within patient score change approach will be used, which defines MCID as the mean change between the outcome scores (NIH EXAMINER Executive composite score) of a group of patients selected per their answers. Second, a sensitivity- and specificity-based approach will be used. This anchor-based approach is useful to calculate the threshold that allows for the best discrimination between groups of patients. The outcome score that produces the greatest and most balanced sensitivity and specificity for discriminating patients with minimal change from patients without any change will be considered as the MCID. Used in conjunction with MCID estimations, sensitivity is the proportion of the patients having change on the external criterion (PD-CFRS) and whose outcome score (NIH EXAMINER Executive composite score) change exceeds the threshold MCID value. Similarly, specificity is the proportion of subjects without any changes on the external criterion (PD-CFRS) and whose outcome changes are below the threshold MCID value. Full, partial and non-responders will be defined using the MCID in both the sham and active rTMS groups (i.e., full = > 1 MCID, partial= 1 MCID, non= < 1 MCID).

The psychometric properties of the PD-CFRS (both self-report and informant report assessed separately) will be assessed using the Rasch model (i.e., construct validity) and concurrent validity will be examined using traditional correlational methods (i.e., concurrent validity with NIH-EXAMINER). For the PD-CFRS, the interrater agreement between self- and informant ratings will be calculated using the Corrected Discrepancy score, which is a rigorous measure correcting for between-subject differences in actual level of scoring.

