Repeated measures/study outcomes are included in a standardized battery of test that will be repeated at baseline, endpoint and follow-up. The battery is expected to take approximately 130 minutes to complete.

Tests administered during screening (e.g., the BDI-II, MoCA, BAI, and HVLT, Memory for Intentions Test, and Modified Fatigue Impact Scale) will not be replicated at baseline, but are included in Table 3 below to indicate it is a repeated measure.

Table 3: Repeated Measures Assessment Tools used in the RCT			
Assessment Name (Abbreviation)	Outcome	Construct measure	Time to complete (min)
NIH-EXAMINER components:	1° (composite score of 7 tests listed below)	Executive function	29 total
Dot counting	2°	Working Memory	7
1-back			5
2-back			5
Flanker	2°	Cognitive Control	5
Set Shifting			5
Letter	2°	Verbal Fluency	1
Category			1
Hopkins Verbal Learning Test-Revised (HVLT)	2°	Memory	10
Symbol Digit Modalities Test (SDMT)	2°	Processing speed	5
The Memory for Intentions Test (MIST)	2°	Prospective memory	15
Monetary-Choice Questionnaire	2°	impulsivity	10
Parkinson's Disease-Cognitive Functional Rating Scale (PD-CFRS)	2°	Real-life function	5
The Activity Measure for Post-Acute Care™ (AM-PAC™) –Applied Cognition questionnaire	2°	Real-life function	10
Timed instrumental activities of daily living (iADL)	2°	Real-life function	15
Beck Depression Inventory-II	2°	Depression	10
Beck Anxiety Inventory	2°	Anxiety	10
Starkstein Apathy Scale	2°	Apathy	5
Montreal Cognitive Assessment	2°	Global Cognition	10
Epworth Sleepiness Scale	2°	Sleepiness	5
Modified Fatigue Impact Scale	2°	Fatigue	5
			Total Time: 144 minutes

Phase 4: Intervention

Participants will be randomized to one of three groups: CCT+PRIIS (n=15), CCT+PRIIS control (n=15) or CCT control +PRIIS control (n=15) and issued a VA iPad to take home and complete the study intervention.

Participants and researchers who are administering and scoring outcome measures will be blinded to group assignment. Effectiveness of blinding will be evaluated by using data collected from mid-point and endpoint questionnaires that assess perception of training intervention⁶⁹. The PI will oversee the RCT and coordinate research procedures and thus will not be blinded to treatment assignments. [name], who will be blinded to group assignments, will coordinate sensitive aspects of the study that require blinding.

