CCT training games are developed by Posit Science Corporation, San Francisco, CA, and are designed to train components of EF specifically affected in PD (Table 5). Participants will be asked to complete, at home, 4 sessions/week for 8 weeks. Each session will take 30min; totaling 16hr of CCT training. No dose effect is established for CCT, thus we looked to the literature^{24,28} and expertise of consultants at Posit Science for guidance on the dose, and determined that 16 hours may be sufficient to detect effects of training on cognition. Progress of the training will not be fixed; training modules will be continuously adaptive, following "staircase" procedures⁷⁰, assuring that success in training on ~75% of exercise trials. While this leads to a

different progression of training across participants, it provides a customized, challenging and internally rewarding training experience that should increase performance motivation and optimize learning⁷¹. CCT active control will include 9 entertaining online games that are played on the same platform as the CCT games (Fig 2). Veterans will be asked to complete, at home, 4 sessions/week for 8wk.

For PRIIS, participants will work with a study team member to determine patient-centered prospective memory tasks. Participants will collaboratively agree on problem areas/areas that they would like to manage better (i.e., remember when to take my medicine) formulated in the form of up to three personal rehabilitation goals using the Bangor Goal-Setting Interview (BGSI)⁷². They will rate their own performance on these goals at initial and follow-up assessments. Participants will be taught to form a 'When X, I will do Y', recite the statement aloud three times, and imaging themselves performing the task during the situation in accordance with the statement for 30 s. In addition to the three patient-centered goals, a common goal for all participants in each group will be completing weekly CCT/CCT active control assignments (e.g., on Monday, Wednesday, and Friday, when I eat lunch, I will complete my cognitive training games).

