PRIIS active control will include verbal rehearsal. These participants will be instructed to recite their prospective memory task (complete weekly intervention assignments) at least three times a day and study them for 30 s. Everyone will be given a handout with strategy instructions as reference. Weekly calls will be made to participants to assess their progress with the prospective memory task of completing weekly intervention assignments. Barriers, facilitators, and resources will be noted and discussed.

The study team member designated as the cognitive coach will make weekly phone calls to the participant to assess compliance and help troubleshoot any difficulties with the assigned programs. During the call, the cognitive coach will help the participant assess their progress with the prospective memory task of completing weekly intervention assignments (and for PRIIS the other goals). Barriers, facilitators, and resources will be discussed.

At midpoint and endpoint (weeks 4 and 8 of the intervention), participant's perception of the training will be assessed, over the phone and by a study team member, with a short questionnaire that will include questions such as: Are the games enjoyable? Are the games challenging? Do you look forward to playing the games? Are you motivated to play the games? Do you think your cognition is improving because of the games? Answers will be rated on a Likert scale. All participants will be reassessed with the neuropsychological battery at endpoint and one month after endpoint. During the one month after endpoint, participants will not be contacted during the one month except to remind them of their appointment for the follow-up assessment.

Specific to the CCT intervention, several factors may contribute to non-compliance with program use. Several elements of flexibility will be incorporated in the treatment schedule to accommodate the challenges that Veterans with PD may encounter. First, the participant may require extra time to complete the program. Participants will be asked to engage in four 30-minute sessions per week for 8 weeks, which is 16 hours in total.

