All participants will complete the assessments listed in Table 3 in a private room with trained research staff at Hines. A semi-structured interview will also be conducted by trained research staff. This interview will take approximately 30 minutes and discussion will focus around feasibility of participating in the study, perception of training for the 2 interventions, usefulness of the weekly cognitive coach calls, and guess at treatment group allocation. We will audiotape this part of the session. The option to consent to audiotaping is included in the veterans's consent form

Phase 6: Follow-up

Follow-up Behavioral Assessments:

One month after the last intervention session, all participants will complete the assessments listed in Table 3 in a private room with trained research staff at Hines.

Unblinding:

Participants will be unblinded after the last participant completes the study. A letter will be mailed to the Veterans.

Knowledgeable informants/caregivers

Knowledgeable informants/caregivers enrolled in the study will be administered the PD-CFRS. Data from the informant will be collected at baseline in person and, to reduce burden of data collection, end-point and follow-up surveys will be mailed to informants for completion. Filling out this form three times (along with an initial demographic form) are the only research procedures performed by the knowledgeable informants/caregivers.

COMPENSATION FOR PARTICIPATION IN RESEARCH ACTIVITIES

Veteran participants will be compensated \$120 for completing all research procedures in this study. Participants will receive \$30 after completing the 2-3 hour long diagnostic confirmation screen. Participants will receive \$30 after completing baseline neuropsychological assessments, \$30 after completing endpoint neuropsychological assessments and \$30 after completing follow-up neuropsychological assessments.

Payment Procedures if screening and/or assessments are completed Hines VA: they will be reimbursed \$30 direct deposit via electronic funds transfer (EFT).

Knowledgeable informants/caregivers will not receive compensation.

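### Does the unstated timing of the anxiety, apathy and depression covariates undermine the group-by-time test of efficacy?

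*Combined protocol and SAP*

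**What the plan says.** Section 5.0 (Neuropsychological Data Analytical Approaches) specifies a two-level mixed model with random subject effects. The covariate sentence is "Covariates will include medication dose, anxiety, apathy, and depression level", followed by "Parameters will be estimated using measurements from baseline, endpoint, and follow-up". The decision rule rests on the group-by-time parameter: "Significance of this parameter will indicate that treatment is efficacious in terms of EF over time when adjusted by covariates". No measurement time is attached to the covariates, and they are not called time-varying.

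Section 1.0, Table 3, lists the Beck Depression Inventory-II, the Beck Anxiety Inventory and the Starkstein Apathy Scale as secondary repeated outcomes. The Phase 3 text uses screening results as the baseline for several scales: "Tests administered during screening (e.g., the BDI-II, MoCA, BAI, and HVLT, Memory for Intentions Test, and Modified Fatigue Impact Scale) will not be replicated". Phase 5 repeats Table 3 at endpoint, and Phase 6 does so again: "One month after the last intervention session, all participants will complete the assessments listed in Table 3". Screening and baseline (Phases 2 and 3) come before randomisation (Phase 4).

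**The concern.** The mood scales are measured at every visit that enters the model, so an analyst could read the covariate sentence as asking for the score at each visit. Post-randomisation scores may be affected by assignment. Adjusting for them removes, or adds, whatever part of the effect runs through mood, and the declared test of efficacy would then answer a different question from the effect of assignment.

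A mood difference between arms is conceivable in either direction. Personal goals belong to the PRIIS arm and are followed up in the weekly calls ("and for PRIIS the other goals"), which might favour it. Against that, "CCT active control will include 9 entertaining online games that are played on the same platform as the CCT games", which might favour control. At stake is whether two analysts following the same sentence could report different estimates for the primary NIH-EXAMINER composite, from a pilot of which Section 3.0 says: "These pilot data will be used as preliminary data for a larger-scale Merit grant proposal".

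**Working it through.** The plan gives no effect size, SD or power figure, so there is nothing of its own to reproduce. The only documented inputs are 3 arms of 15 and 3 visits (Section 1.0) and the model form (Section 5.0). All other inputs below are assumptions.

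**1. Baseline reading.** The group-by-time parameter is a difference between arms in within-subject change. A covariate that is constant within a subject cancels from every change score. In complete data the estimate therefore cannot move. Simulation agrees: over 2,000 trials per case at 15 per arm, the estimates with no covariate and with baseline mood differ by at most 2e-14. With an assumed 20% drop-out, the estimate changes by 0.008 on average against an SE of 0.34.

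**2. Visit-level reading.** Let T be the total effect, d the effect of assignment on mood (higher score is worse) and b the slope of cognition on mood. With an error-free scale and no shared time-varying cause,

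adjusted parameter = T − b × d.

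For T = 0.5, d = −0.2, b = −0.2: 0.5 − 0.04 = 0.46. For d = −0.3, b = −0.3: 0.5 − 0.09 = 0.41. For d = 0 it stays at 0.5.

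The simulation used a random-intercept model with one mood covariate, between- and within-subject variances of 0.6 and 0.4, and T = 0.5 SD for CCT+PRIIS against double control from baseline to endpoint. Visit-level minus baseline-covariate estimate:

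| d | b | Error-free scale | Reliability 0.8 |
|---|---|---|---|
| −0.3 | −0.2 | −0.059 | −0.041 |
| −0.3 | −0.3 | −0.087 | −0.061 |
| −0.2 | −0.2 | −0.042 | −0.031 |
| −0.2 | −0.3 | −0.060 | −0.043 |
| 0 | −0.2 | 0.000 | +0.001 |
| 0 | −0.3 | −0.002 | 0.000 |
| +0.2 | −0.2 | +0.039 | +0.027 |
| +0.2 | −0.3 | +0.060 | +0.044 |
| +0.3 | −0.2 | +0.061 | +0.042 |
| +0.3 | −0.3 | +0.088 | +0.060 |

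**3. Size against the trial's own noise.** Two arms, each with a two-visit change, give SE = sqrt(4 × 0.4 / 15) = 0.327. For non-zero d, the smallest and largest shifts are 0.027 / 0.327 = 0.08 and 0.088 / 0.327 = 0.27 of an SE. At reliability 0.8 the two models disagree on p < 0.05 in 5–10% of trials. Of this, 5–8% appears with no mood effect at all, so most of it is chance difference in mood change rather than bias.

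**4. Larger assumptions.** With d = −0.5 and b = −0.4 the expected shift is 0.5 × 0.4 = 0.20. In one simulated dataset of 15 per arm with those inputs, the estimate was 0.3552 (SE 0.3058) both without a covariate and with baseline mood, and 0.019 (SE 0.2508) with visit-level mood. A shared time-varying cause of mood and cognition widens the gap: 0.537 against 0.270 in one dataset of 500 per arm. The visit-level reading is therefore not harmless in every case, but nothing in the documents points to inputs of that size.

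**5. What the text suggests.** Section 5.0 names depression, anxiety, apathy and L-dopa equivalent dose again as candidate moderators, beside age, age at onset, disease duration and MoCA score. These are mostly characteristics at entry. The list also includes training-perception scores, which are post-randomisation, so this is a hint and not proof. For medication dose, Section 1.0 admits only patients expected to stay on stable medication, so the two readings should nearly coincide. The entry cut-offs (BDI-II 29–63, BAI 12 or more and Starkstein 14 or more are withdrawn) leave limited room for improvement, especially on anxiety and apathy.

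**The case for a change.** The strongest case for a change is that the visit-level reading is natural in a longitudinal model whose covariates are measured at every visit. With complete data it is also the only main-effect reading under which adjustment alters the tested parameter. Choosing between readings after seeing the data is avoidable, the repair is a few words, and the precision given up is slight: SE 0.325–0.326 with baseline mood, against 0.318–0.324 with visit-level mood at reliability 0.8.

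Part of this stands. The timing is not stated, no passage limits the covariates to baseline, and the two readings can differ in a single trial. The rest is weaker. That baseline covariates leave this parameter unmoved shows that the adjustment is redundant there; it does not show that visit-level values were intended. Prognostic baseline terms are routinely listed in such models and do no harm. Low cost alone does not turn an unstated detail into a fault when the customary reading gives a sound analysis. Nor would baseline terms be what protects the total effect, since a model with no mood covariate estimates it equally well. What matters is leaving post-randomisation values out, and the plan never says to put them in.

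**Conclusion.** No change follows. The plan leaves a covariate definition unstated, and an analyst of a randomised trial would fill it with values from before randomisation, which are already collected. Read that way, the group-by-time parameter remains the total effect of assignment: the complete-data estimate is identical to the unadjusted one, and the average difference is 0.008 under an assumed 20% drop-out.

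Bias requires three things together: visit-level entry, an effect of assignment on mood, and a non-zero mood–cognition slope. The documents establish none of them. If all three held at the moderate values assumed here, the average shift would be 5–18% of an effect of 0.5 SD, in either direction, or about 0.1 to 0.3 SE in a pilot of 15 per arm. These figures rest on assumed variances, slopes and reliability, and on one mood covariate where the plan has three plus dose. They illustrate the scale and do not estimate the shift. Larger assumed mood effects would give larger shifts.

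If a mood scale is itself modelled as an outcome, the analyst would leave it out as a covariate. The text of Aims 2 and 3 is not in the document reviewed, so whether that arises cannot be settled here.

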1.0 Study Design and Methods

Study Design

To address the study objectives, a pilot randomized controlled trial will be conducted.

Study population:

Group 1: Veterans

A convenience sample of Veterans , who are screened and diagnosed with Parkinson's disease (PD) and mild cognitive impairment in the executive function domain will be enrolled. Targeted enrollment for the intervention is 45; they will be randomized to one of three groups: CCT+PRIIS (n=15), CCT+PRIIS control (n=15) or CCT control +PRIIS control (n=15).

Group 2: Knowledgeable Informants

We will also enroll knowledgeable informants/caregivers of the enrolled Veterans. Thus, we will be enrolling civilians (however it is possible that caregiver could be a Veteran and this is acceptable). The purpose for enrolling a caregiver is to obtain their perspective on functional changes related to cognitive impairment in the Veteran living with PD. To obtain their perspective, they will complete the PD-Cognitive Functional Rating Scale (PD-CFRS) at three different time points during the study. The planned activities for the caregiver are the following: consent, demographic form, PD-CFRS at three different time points. The consent form, demographic form and PD-CFRS will be completed at their first visit. We will mail them the form when their Veteran completes the RCT, we will mail them the form again one month later. A knowledgeable informant/caregiver is not required in order for the Veterans to enroll. Targeted enrollment is 45, however we anticipate having to enroll 60 civilians due to Veterans being withdrawn – and thus the associated civilian will need to be withdrawn.

Below we list the inclusion and exclusion criteria for both Veterans and Knowledgeable Informants.

Group 1: Veterans

In general, eligibility criteria target Veterans with idiopathic PD and not other forms of parkinsonism. Thus, only Veterans older than 50 with PD diagnosed according to UK Parkinson's Disease Society Brain Bank

Diagnostic Criteria will be eligible. PD medication can influence cognitive function, thus, only participants receiving stable medication (i.e., no changes in medication or dose for the past month) and who are expected to remain on stable medication for the duration of the RCT will be eligible.

Inclusion criteria for Veterans:

- Diagnosis of PD as determined by the UK Parkinson's Disease Society Brain Bank Diagnostic Criteria⁴⁶
- age 50 and older

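### The group-by-time analysis compares raw changes from each arm's own baseline; it should set one common baseline mean or adjust for the baseline score

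*Combined protocol and SAP*

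**What the plan says.** Section 5.0, Neuropsychological Data Analytical Approaches, specifies for Aims 2 and 3 a "two-level longitudinal mixed effects model with random subject effects to incorporate correlation of measurements nested within the same subject". On the data that enter it: "Parameters will be estimated using measurements from baseline, endpoint, and follow-up". On efficacy: "The group by time interaction parameter will be used to examine the difference of the trends between the three groups", with significance of that parameter read as evidence that treatment works. For the immediate effect, "an experiment group contrast will be formed using test score means at baseline and endpoint"; the controls get a matching contrast, built the same way. On adjustment: "Covariates will include medication dose, anxiety, apathy, and depression level".

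The outcome's own baseline value is not among the covariates, and nothing states that the arms share a baseline mean. ANCOVA is named in Section 5.0 only for checking that the groups are comparable on descriptive variables.

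Section 1.0 gives three arms of 15 and describes no stratification on baseline score. Table 3 makes the NIH-EXAMINER composite the primary outcome. Baseline testing is Phase 3 and randomisation is Phase 4.

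**The concern.** Under this specification each arm has its own freely estimated baseline mean, and that mean is subtracted from the arm's later mean. Because baseline precedes randomisation, the three true baseline means are equal and any observed difference is chance. Subtracting the whole of that difference removes too much, since a Veteran who starts high is expected to regress part of the way towards the mean. The resulting estimate is noisier than the data require and, in a given trial, shifts against the arm that happened to start higher.

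The listed covariates do not repair this. If they are baseline values, they are constant within a Veteran and cancel from every within-person contrast when data are complete. The outcome's own baseline score, likely the strongest predictor, is collected but not used for adjustment.

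At stake is precision, which a 45-Veteran pilot has little of. The same model is to be reported for every outcome in Aims 2 and 3, and Section 3.0 says the results will support a larger grant proposal.

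**Working it through.** The plan gives no power statement, effect size, SD or correlation for the composite, so there is no stated figure to reproduce.

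**Inputs.** From Section 1.0: n = 15 per arm, three arms, three visits. Assumed: outcome SD = 1 at every visit, complete data, and baseline-to-endpoint correlation rho from 0.5 to 0.9.

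**Step 1: is the planned contrast a change score?** With time as a category, complete data and covariates fixed at baseline, the baseline-to-endpoint group-by-time estimate is

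(endpoint mean − baseline mean) in one arm − (endpoint mean − baseline mean) in the other.

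A random-intercept model was fitted to 900 simulated trials (3 × 15 Veterans, 3 visits, 300 trials at each of rho 0.5, 0.7 and 0.85). The estimate equalled the raw difference in mean change every time; the largest gap was about 6 × 10⁻¹⁵.

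If time is instead a linear trend over weeks 0, 8 and 12 (taking one month as four weeks), the slope weights are proportional to each week minus the mean of 6.67: −6.67, 1.33 and 5.33. They sum to zero and the largest falls on the arm's own baseline, so the same weakness remains.

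**Step 2: variances for one pair of arms.**

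- Change score: 2(1 − rho) × 2/15
- Common baseline mean, or baseline as covariate: (1 − rho²) × 2/15
- Ratio: (1 − rho²) / [2(1 − rho)] = (1 + rho)/2
- Arm size the planned contrast would need to match 15 per arm after the fix: 15 × 2/(1 + rho)

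At rho 0.7 the variances are 0.6 × 0.1333 = 0.080 (SE 0.283) and 0.51 × 0.1333 = 0.068 (SE 0.261).

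| rho | SE planned | SE adjusted | Variance ratio | Matching n per arm | Detectable difference, 80% power (SD units) |
|---|---|---|---|---|---|
| 0.5 | 0.365 | 0.316 | 0.75 | 20.0 | 1.02 → 0.89 |
| 0.6 | 0.327 | 0.292 | 0.80 | 18.8 | 0.91 → 0.82 |
| 0.7 | 0.283 | 0.261 | 0.85 | 17.6 | 0.79 → 0.73 |
| 0.8 | 0.231 | 0.219 | 0.90 | 16.7 | 0.65 → 0.61 |
| 0.9 | 0.163 | 0.159 | 0.95 | 15.8 | 0.46 → 0.45 |

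The last column uses a normal approximation with two-sided alpha 0.05 (sidedness is not stated in the plan).

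**Step 3: small-sample cost.** Estimating a baseline slope inflates the ANCOVA variance by about 1 + 1/(45 − 3 − 2) = 1.025. The ratios become 0.75 × 1.025 = 0.77 at rho 0.5, 0.85 × 1.025 = 0.87 at 0.7 and 0.95 × 1.025 = 0.97 at 0.9. In 40,000 simulated trials per value of rho, the common-baseline analysis (using an estimated pooled correlation) gave 0.76, 0.86, 0.91 and 0.96 at rho 0.5, 0.7, 0.8 and 0.9. ANCOVA gave 0.77, 0.87, 0.92 and 0.98.

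**Step 4: chance imbalance.** The baseline difference between two arms has SD √(2/15) = 0.365 outcome SDs. A gap above 0.5 SD has probability 0.17 for a given pair and 0.36 for at least one of the three pairs. The planned estimate moves with the gap at slope −(1 − rho); after the fix the slope is about zero. A gap of one standard error therefore shifts the planned estimate by 0.5 × 0.365 = 0.18 SD at rho 0.5, 0.3 × 0.365 = 0.11 at 0.7 and 0.1 × 0.365 = 0.04 at 0.9.

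**The case against.** The strongest reply is that the plan is under-specified rather than wrong. No model equation is written, and treating baseline as an outcome is compatible with a common-baseline model. That stands as a limit on certainty. But the contrasts built from each group's own baseline mean point to separate baseline means, and if a common mean was intended, the text still has to say so.

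Second, Section 5.0 does not say that the mood covariates are baseline values, and Table 3 lists depression, anxiety and apathy as repeated measures. Entered as time-varying they would not cancel, and the exact identity with change scores would fail. This also stands. They would then be post-randomisation measurements, however, and would still not adjust for the baseline composite.

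Third, the gain is modest and depends on an unknown rho. Intervals narrow by about 8% at rho 0.7 (0.283 to 0.261) and by 2 to 3% at rho 0.9. Detectable differences stay large unless rho is high.

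Fourth, nothing is invalid. Under randomisation the planned contrast is unbiased on average and keeps its type I error; the over-correction is conditional on the imbalance observed. That is correct, and it makes this an efficiency point. It does not argue against a remedy that is nearly free.

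**Conclusion.** The concern holds. On the plain reading of Section 5.0, the immediate-effect comparison is a change-score comparison that does not use the equality of baseline means created by randomisation. The loss is one of precision, not validity. The avoidable variance is about 25% at rho 0.5, 15% at 0.7 and 5% at 0.9, slightly less after the small-sample cost. In addition, the estimate depends on chance baseline gaps that will often be appreciable at 15 per arm.

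These figures assume a separate baseline mean per arm, complete data, categorical time, covariates fixed at baseline and equal SD across visits. The documents supply no rho, so the range should be read as a whole. The change should be made; the trial can be analysed validly without it.

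**What to change.** State one of two equivalent approaches in Section 5.0:

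1. Keep all three visits as outcomes in Proc Mixed, but remove the group main effect at baseline so that the three arms share one baseline mean. Keep group-by-visit terms at endpoint and at follow-up.
2. Model only endpoint and follow-up as outcomes, with the baseline score and its interaction with visit as covariates.

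In either case, report the between-arm differences at endpoint and follow-up as the efficacy estimates, in place of the difference in trends. The endpoint-to-follow-up contrasts for sustainability do not involve baseline and can still be formed from the same fit. State also that the mood and medication covariates are the pre-randomisation values. For HVLT, MIST, MoCA, depression, anxiety and fatigue, Phase 3 already makes the screening value the baseline, and it too precedes randomisation.

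The cost is a few sentences of SAP wording and a changed model statement, settled before the data are unblinded. It needs no new data, visits or Veterans, and simulated type I error with baseline adjustment stayed at about 0.05.
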